#### 5.2.2 Vital signs

Systolic and diastolic blood pressures (BP) as well as pulse rate (PR) or heart rate (heart rate is considered to be equal to pulse rate) will be measured by a blood pressure monitor (Dinamap Pro 100, at the times indicated in the Flow Chart, after subjects have rested for at least 5 min in a supine position. All recordings should be made using the same type of blood pressure recording instrument on the same arm, if possible.

Body temperature will be measured orally or under the armpit (axillary method) or in the ear (tympanic method) at each ambulatory visit, at admission to the trial site, and each day in the morning during in-house stay (refer to Flow Chart).

#### 5.2.3 Ophthalmological examination

A slit lamp examination (e.g. RSL 110) will be conducted by an ophthalmologist at Screening and EoTrial examination to exclude findings suspicious for signs of cataract and/or other ocular disorders.

Data from ophthalmological examination will not be transferred to the CRF/database, only abnormal findings will be recorded as AEs if judged clinically relevant by the Investigator.

#### 5.2.4 Safety laboratory parameters

For the assessment of laboratory parameters, blood and urine samples will be collected by the trial site at the times indicated in the Flow Chart after the subjects have fasted for at least 10 h. For retests, at the discretion of the investigator or designee, overnight fasting is not required.

The parameters that will be determined are listed in Tables 5.2.4:1 and 5.2.4:2. Reference ranges will be provided in the ISF, Section 10.

Page 44 of 75

Proprietary confidential information © 2021 Boehringer Ingelheim International GmbH or one or more of its affiliated companies

Manual differential white blood cell count will be performed if there is an abnormality detected with the automatic blood cell count. Urine microscopic examinations will be performed in addition to urinalysis (Stix) in order to correctly evaluate possible abnormalities detected at the urinalysis (Stix).

Table 5.2.4: 1 Routine laboratory tests

Functional lab group	BI test name [comment/abbreviation]	A	В	С
Haematology	Haematocrit	X	X	X
	Haemoglobin	X	X	X
	Red Blood Cell Count (Erythrocytes), absol.	X	X	X
	Reticulocytes, absol.	X	X	X
	White Blood Cells (Leucocytes), absol.	X	X	X
	Platelet Count (Thrombocytes), absol.	X	X	X
Automatic WBC	Neutrophils/ Leukocytes; Eosinophils/ Leukocytes;	X	X	X
differential, relative	Basophils/ Leukocytes; Monocytes/ Leukocytes;			
ŕ	Lymphocytes/ Leukocytes			
Automatic WBC	Neutrophil, absol.; Eosinophils, absol.; Basophils, absol.;	37	37	37
differential, absolute	Monocytes, absol.; Lymphocytes, absol.	X	X	X
Manual differential	Neut. Poly (segs); Neut. Poly (segs), absol.; Neutrophils			
WBC (if automatic	Bands; Neutrophils Bands, absol.; Eosinophils/ Leukocytes;			
differential WBC is	Eosinophils, absol.; Basophils/ Leukocytes; Basophils, absol.;			
abnormal)	Monocytes/ Leukocytes; Monocytes, absol.; Lymphocytes/			
,	Leukocytes; Lymphocytes, absol.			
Coagulation	Activated Partial Thromboplastin Time	X	X	X
8	Prothrombin time – INR (International Normalization Ratio)	X	X	X
	Fibrinogen	X	X	X
Enzymes	AST [Aspartate transaminase] /GOT, SGOT	X	X	X
	ALT [Alanine transaminase] /GPT, SGPT	X	X	X
	Alkaline Phosphatase	X	X	X
	Gamma-Glutamyl Transferase	X	X	X
	Creatine Kinase [CK]	X	X	X
	Creatine Kinase Isoenzyme MB [only if CK is elevated]	X	X	X
	Lactic Dehydrogenase	X	X	X
	Lipase	X	X	X
	Amylase	X	X	X
Substrates	Glucose (Plasma)	X	X	X
	Creatinine	X	X	X
	Bilirubin, Total	X	X	X
	Bilirubin, Direct	X	X	X
	Protein, Total	X	X	X
	Albumin		X	X
	Albumin (Protein Electrophoresis)	X		
	Alpha-1-Globulin (Protein Electrophoresis)	X		
	Alpha-2-Globulin (Protein Electrophoresis)	X		
	Beta-Globulin (Protein Electrophoresis)	X		
	Gamma-Globulin (Protein Electrophoresis)	X		
	C-Reactive Protein (Quant)	X	X	X
	Uric Acid	X	X	X
	Cholesterol, total	X	X	X
	Triglyceride	X	X	X

Page 45 of 75

Proprietary confidential information © 2021 Boehringer Ingelheim International GmbH or one or more of its affiliated companies

Table 5.2.4.: 1 Routine laboratory tests (cont.)

Functional lab group	BI test name [comment/abbreviation]	A	В	С
Hormones	Thyroid Stimulating Hormone	X		
	Free T3 - Triiodothyronine	X		
	Free T4 – Thyroxine	X		
Electrolytes	Sodium	X	X	X
	Potassium	X	X	X
	Calcium	X	X	X
Urinalysis (Stix)	Urine Nitrite (qual)	X	X	X
	Urine Protein (qual)	X	X	X
	Urine Glucose (qual)	X	X	X
	Urine Ketone (qual)	X	X	X
	Urobilinogen (qual)	X	X	X
	Urine Bilirubin (qual)	X	X	X
	Urine RBC/Erythrocytes (qual)	X	X	X
	Urine WBC/Leucocytes (qual)	X	X	X
	Urine pH	X	X	X
Urine sediment	Only positive findings will be reported (for instance, the			
(microscopic	presence of sediment bacteria, casts in sediment, squamous			
examination if	epithelial cells, erythrocytes, leukocytes)			
erythrocytes,				
leukocytes nitrite or				
protein are abnormal				
in urine)				

A: parameters to be determined at Visit 1 (screening examination)

The tests listed in Table 5.2.4: 2 are exclusionary laboratory tests that may be repeated as required. The results will not be entered in the CRF/database and will not be reported in the CTR. Drug screening will be performed at screening and after admission to the trial site. Infectious serology will be performed at screening only.

B: parameters to be determined at Visit 1 on Day -3 to -1; and on Day 2 and Day 5 in each treatment period (i.e. at Visits 2 and 3) (for time points refer to Flow Chart)

C: parameters to be determined at Visit 4 (end of trial examination)

c34388550-04 Trial Protocol Page 46 of 75

Proprietary confidential information © 2021 Boehringer Ingelheim International GmbH or one or more of its affiliated companies

Table 5.2.4: 2 Exclusionary laboratory tests

Functional lab group	Test name
Drug screening (urine)	Amphetamine/MDA Barbiturates Benzodiazepine Cannabis Cocaine Methadone Methamphetamines/MDMA/XTC Opiates Tricyclic antidepressants
Infectious serology (blood)	Hepatitis B surface antigen (qualitative) Hepatitis B core antibody (qualitative) Hepatitis C antibodies (qualitative) HIV-1 and HIV-2 antibody (qualitative)
COVID-19 ¹	SARS CoV-2 PCR test

¹ evaluation will be performed shortly (within 72 hours) before admission to trial site in each treatment period as per Flow Chart

To encourage compliance with alcoholic restrictions, a breath alcohol test (e.g. Alcotest[®] 6510 and Alcotest[®] 5510, will be performed at admission to the trial site, and may be repeated at any time during the study at the discretion of an investigator or designee. The results will not be included in the CTR.

The laboratory tests listed in Tables 5.2.4: 1 and 5.2.4: 2 will be performed at , with the exception of drug screening. These tests will be performed at the trial site using e.g. Triage® TOX Drug Screen, or Combur9 Test®, or comparable test systems. SARS-CoV-2 virus PCR test will be performed either by or the trial site.

Laboratory data will be transmitted electronically from the laboratory to the trial site.

#### 5.2.5 Electrocardiogram

Twelve-lead ECGs (I, II, III, aVR, aVL, aVF, V1 - V6) will be recorded using a computerised electrocardiograph (CardioSoft EKG System,

at the times provided in the Flow Chart. Electrode placement will be performed according to the method of Wilson, Goldberger and Einthoven modified by Mason and Likar (hips and shoulders instead of ankles and wrists). Precise electrode placement will be marked with an indelible mark on the skin to allow reproducible placement throughout the study.

To achieve a stable heart rate at rest and to assure high quality recordings, the site personnel will be instructed to assure a relaxed and quiet environment, so that all subjects are at complete rest.

All ECGs will be recorded for a 10 sec duration after subjects have rested for at least 5 min in a supine position. ECG assessment will always precede all other study procedures scheduled for the same time (except for blood drawing from an intravenous cannula that is already in place) to avoid compromising ECG quality.

c34388550-04 Trial Protocol Page 47 of 75

Proprietary confidential information © 2021 Boehringer Ingelheim International GmbH or one or more of its affiliated companies

All ECGs will be stored electronically at the site.

All locally printed ECGs will be evaluated by the investigator or a designee. Abnormal findings will be reported as AEs (during the trial) or baseline conditions (at screening) if assessed to be clinically relevant by the investigator. Any ECG abnormalities will be carefully monitored and, if necessary, the subject will be removed from the trial and will receive the appropriate medical treatment.

ECGs may be repeated for quality reasons (for instance, due to alternating current artefacts, muscle movements, or electrode dislocation) and the repeated ECG will be used for analysis. Additional (unscheduled) ECGs may be collected by the investigator for safety reasons.

#### 5.2.6 Other safety parameters

Not applicable.

#### 5.2.7 Assessment of adverse events

#### 5.2.7.1 Definitions of adverse events

#### 5.2.7.1.1 Adverse event

An adverse event (AE) is defined as any untoward medical occurrence in a patient or clinical investigation subject administered a medicinal product and which does not necessarily have to have a causal relationship with this treatment.

An AE can therefore be any unfavourable and unintended sign (including an abnormal laboratory finding), symptom, or disease temporally associated with the use of a medicinal product, whether or not considered related to the medicinal product.

The following should also be recorded as an AE in the CRF and BI SAE form (if applicable):

- Worsening of the underlying disease or of other pre-existing conditions
- Changes in vital signs, ECG, physical examination, and laboratory test results, if they are judged clinically relevant by the investigator

If such abnormalities already pre-exist prior to trial inclusion, they will be considered as baseline conditions and should be collected in the eCRF only.

#### 5.2.7.1.2 Serious adverse event

A serious adverse event (SAE) is defined as any AE which fulfils at least one of the following criteria:

- Results in death
- Is life-threatening, which refers to an event in which the patient was at risk of death at the time of the event; it does not refer to an event that hypothetically might have caused death if more severe
- Requires inpatient hospitalisation
- Requires prolongation of existing hospitalisation

Page 48 of 75

Proprietary confidential information © 2021 Boehringer Ingelheim International GmbH or one or more of its affiliated companies

- Results in persistent or significant disability or incapacity
- Is a congenital anomaly/birth defect
- Is deemed serious for any other reason if it is an important medical event when based upon appropriate medical judgment which may jeopardise the patient and may require medical or surgical intervention to prevent one of the other outcomes listed in the above definitions. Examples of such events are intensive treatment in an emergency room or at home for allergic bronchospasm, blood dyscrasias or convulsions that do not result in hospitalisation or development of dependency or abuse

#### 5.2.7.1.3 AEs considered 'Always Serious'

Cancers of new histology and exacerbations of existing cancer must be classified as a serious event regardless of the time since discontinuation of the trial medication and must be reported as described in Section 5.2.7.1.9 and Section 5.2.7.1.10, subsections 'AE Collection' and 'AE **reporting to sponsor and timelines**'.

In accordance with the European Medicines Agency initiative on Important Medical Events, Boehringer Ingelheim has set up a list of further AEs, which, by their nature, can always be considered to be 'serious' even though they may not have met the criteria of an SAE as defined above.

The latest list of 'Always Serious AEs' can be found in the eDC system, an electronic data capture system which allows the entry of trial data at the trial site. These events should always be reported as SAEs as described above.

#### 5.2.7.1.4 Adverse events of special interest

The term adverse events of special interest (AESI) relates to any specific AE that has been identified at the project level as being of particular concern for prospective safety monitoring and safety assessment within this trial, e.g. the potential for AEs based on knowledge from other compounds in the same class. AESIs need to be reported to the sponsor's Pharmacovigilance Department within the same timeframe that applies to SAEs, please see Section 5.2.7.1.10.

The following are considered as AESIs:

#### • Hepatic injury

A hepatic injury is defined by the following alterations of hepatic laboratory parameters:

- o An elevation of AST (aspartate transaminase) and/or ALT (alanine transaminase) ≥3-fold ULN combined with an elevation of total bilirubin ≥2-fold ULN measured in the same blood sample, or
- o Aminotransferase (ALT, and/or AST) elevations ≥10 fold ULN

These lab findings constitute a hepatic injury alert and the subjects showing these lab abnormalities need to be followed up according to the 'DILI checklist' provided in the ISF. In case of clinical symptoms of hepatic injury (icterus, unexplained encephalopathy, unexplained coagulopathy, right upper quadrant abdominal pain,

c34388550-04 Trial Protocol Page 49 of 75

Proprietary confidential information © 2021 Boehringer Ingelheim International GmbH or one or more of its affiliated companies

etc.) without lab results (ALT, AST, total bilirubin) available, the Investigator should make sure that these parameters are analysed, if necessary in an unscheduled blood test. Should the results meet the criteria of hepatic injury alert, the procedures described in the DILI checklist should be followed.

## 5.2.7.1.5 Intensity (severity) of AEs

The intensity (severity) of the AE should be judged based on the following:

Mild: Awareness of sign(s) or symptom(s) that is/are easily tolerated Moderate: Sufficient discomfort to cause interference with usual activity

Severe: Incapacitating or causing inability to work or to perform usual activities

#### 5.2.7.1.6 Causal relationship of AEs

Medical judgment should be used to determine the relationship, considering all relevant factors, including pattern of reaction, temporal relationship, de-challenge or re-challenge, confounding factors such as concomitant medication, concomitant diseases and relevant history.

Arguments that may suggest that there is a reasonable possibility of a causal relationship could be:

- The event is consistent with the known pharmacology of the drug
- The event is known to be caused by or attributed to the drug class
- A plausible time to onset of the event relative to the time of drug exposure
- Evidence that the event is reproducible when the drug is re-introduced
- No medically sound alternative aetiologies that could explain the event (e.g. preexisting or concomitant diseases, or co-medications)
- The event is typically drug-related and infrequent in the general population not exposed to drugs (e.g. Stevens-Johnson syndrome)
- An indication of dose-response (i.e. greater effect size if the dose is increased, smaller effect size if dose is reduced)

Arguments that may suggest that there is no reasonable possibility of a causal relationship could be:

- No plausible time to onset of the event relative to the time of drug exposure is evident (e.g. pre-treatment cases, diagnosis of cancer or chronic disease within days / weeks of drug administration; an allergic reaction weeks after discontinuation of the drug concerned)
- Continuation of the event despite the withdrawal of the medication, taking into account the pharmacological properties of the compound (e.g. after 5 half-lives). Of note, this criterion may not be applicable to events whose time course is prolonged despite removing the original trigger

Proprietary confidential information © 2021 Boehringer Ingelheim International GmbH or one or more of its affiliated companies

- Additional arguments amongst those stated before, like alternative explanation (e.g. situations where other drugs or underlying diseases appear to provide a more likely explanation for the observed event than the drug concerned)
- Disappearance of the event even though the trial drug treatment continues or remains unchanged
  - 5.2.7.2 Adverse event collection and reporting

#### 5.2.7.2.1 AE collection

Upon enrolment into a trial, the subject's baseline condition is assessed (for instance, by documentation of medical history/concomitant diagnoses), and relevant changes from baseline are noted subsequently.

Subjects will be required to report spontaneously any AEs as well as the time of onset, end time, and intensity of these events. In addition, each subject will be regularly assessed by the medical staff throughout the clinical trial and whenever the investigator deems necessary. As a minimum, subjects will be questioned for AEs (and concomitant therapies) at the time points indicated in the Flow Chart. Assessment will be made using non-specific questions such as 'How do you feel?'. Specific questions will be asked wherever necessary in order to more precisely describe an AE.

A carefully written record of all AEs shall be kept by the investigator in charge of the trial. Records of AEs shall include data on the time of onset, end time, intensity of the event, and any treatment or action required for the event and its outcome.

The following must be collected and documented on the appropriate CRF(s) by the investigator:

- From signing the informed consent onwards until an individual subject's end of trial:
  - o All AEs (serious and non-serious) and all AESIs
  - The only exception to this rule are AEs (serious and non-serious) and AESIs in Phase I trials in healthy volunteers, when subjects discontinue from the trial due to screening failures prior to administration of any trial medication. In these cases, the subjects' data must be collected at trial site but will not be entered in the CRF or trial database and will not be reported in the CTR.
- After the individual subject's end of trial:
  - o The investigator does not need to actively monitor the subject for AEs but should only report any occurrence of cancer and related SAEs and related AESIs of which the investigator may become aware of by any means of communication, e.g. phone call. Those AEs should, however, not be reported in the CRF.

30 June 2021

c34388550-04 Trial Protocol Proprietary confidential information © 2021 Boehringer Ingelheim International GmbH or one or more of its affiliated companies

#### 5.2.7.2.2 AE reporting to the sponsor and timelines

The Investigator must report SAEs, AESIs, and non-serious AEs which are relevant for the reported SAE or AESI, on the BI SAE form via fax immediately (within 24 hours) to the sponsor's unique entry point (country specific contact details will be provided in the ISF). The same timeline applies if follow-up information becomes available. In specific occasions the Investigator could inform the sponsor upfront via telephone. This does not replace the requirement to complete and fax the BI SAE form.

With receipt of any further information to these events, a follow-up SAE form has to be provided. For follow-up information, the same rules and timeline apply as for initial information.

#### 5.2.7.2.3 Information required

All (S)AEs, including those persisting after the individual subject's end of trial, must be followed up until they have resolved, have been sufficiently assessed as 'chronic' or 'stable', or no further information can be obtained.

#### 5.2.7.2.4 Pregnancy

Once the male subject has been enrolled in the clinical trial and has taken trial medication, and if a partner of the male trial participant becomes pregnant, the investigator must report any drug exposure during pregnancy in a partner of the male trial participant immediately (within 24 hours) by means of Part A of the Pregnancy Monitoring Form to the sponsor's unique entry point, after a written consent of the pregnant partner.

The outcome of the pregnancy associated with the drug exposure during pregnancy must be followed up and reported to the sponsor's unique entry point on the Pregnancy Monitoring Form for Clinical Trials (Part B).

The ISF will contain the Pregnancy Monitoring Form for Clinical Trials (Part A and Part B) as well as non-trial specific information and consent for the pregnant partner.

As pregnancy itself is not to be reported as an AE, in the absence of an accompanying SAE and/or AESI, only the Pregnancy Monitoring Form for Clinical Trials and not the SAE form is to be completed. If there is an SAE and/or AESI associated with the pregnancy, an SAE form must be completed in addition.

# 5.3 DRUG CONCENTRATION MEASUREMENTS AND PHARMACOKINETICS

#### **5.3.1** Assessment of pharmacokinetics

For the assessment of pharmacokinetics, blood samples will be collected at the time points indicated in the Flow Chart. The actual sampling times will be recorded and used for determination of pharmacokinetic parameters.

Page 52 of 75

Proprietary confidential information © 2021 Boehringer Ingelheim International GmbH or one or more of its affiliated companies

Date and clock times of drug administration and pharmacokinetic sampling will be recorded in the CRFs. The actual sampling times will be used for determination of pharmacokinetic parameters.

#### 5.3.2 Methods of sample collection

#### 5.3.2.1 Blood sampling for pharmacokinetic analysis

For quantification of BI 1595043 concentrations in plasma, 2.7 mL of blood will be drawn from an antecubital or forearm vein into an K₂-EDTA (dipotassium ethylenediaminetetraacetic acid)-anticoagulant blood drawing tube at the times indicated in the Flow Chart. Blood will be withdrawn by means of either an indwelling venous catheter or by venepuncture with a metal needle.

The EDTA-anticoagulated blood samples will be centrifuged for approximately 10 min at approximately 2000 g to 4000 g and at 4 to 8 °C. Two plasma aliquots will be obtained and stored in polypropylene tubes. The first aliquot should contain at least 0.5 mL of plasma, the second aliquot will contain the remaining plasma. The process from blood collection until transfer of plasma aliquots into the freezer should be completed in less than 90 min, with interim storage of blood samples and aliquots at room temperature. The time each aliquot was placed in the freezer will be documented. Until transfer on dry ice to the analytical laboratory, the aliquots will be stored upright at approximately -20°C or below at the trial site. The second aliquot will be transferred to the analytical laboratory after the bioanalyst has acknowledged safe arrival of the first aliquot. At the analytical laboratory, the plasma samples will be stored at approximately -20°C or below until analysis.

At a minimum, the sample tube labels should list BI trial number, subject number, day, and planned sampling time. Further information such as matrix and analyte may also be provided.

Plasma samples will be transferred to

After completion of the trial, the plasma samples may be used for further methodological investigations (e.g., assessment of metabolites). However, only data related to the analyte and/or its metabolite(s) will be generated by these additional investigations. The study samples will be discarded after completion of the additional investigations, but not later than 5 years after the CTR is archived.

Boehringer Ingelheim BI Trial No.: 1445-0011 30 June 2021

Page 53 of 75

Proprietary confidential information © 2021 Boehringer Ingelheim International GmbH or one or more of its affiliated companies

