a w			08:00	16:00	Snack (voluntary) ³		X		X	X
d by			10:00	18:00	Dinner ³					
rate			12:00	20:00			X		X	X
epa		2	24:00	08:00	Breakfast ³	В	X	X	x ¹¹	X
s sp			29:00	13:00	Lunch					
eric			32:00	16:00	Snack (voluntary)					
al p			34:00	18:00	Dinner ³		X			X
1/2 (two identical periods separated by a washout of at least 8 days between drug administrations)		3	48:00	08:00	Confirmation of fitness and discharge from trial site, breakfast ³		Х		x ¹¹	Х
.wo		4	72:00	08:00	Ambulatory visit		X		x ¹¹	X
/2 (t		5	96:00	08:00	Ambulatory visit	В	X		x ¹¹	X
1.		6	120:00	08:00	Ambulatory visit		X		x ¹¹	X
		7	144:00	08:00	Ambulatory visit		X		x ¹¹	X
		8	168:00	08:00	Ambulatory visit		X		x ¹¹	X
EoT	4	9 - 14			End of trial (EoTrial) examination ⁴	C		X	x ¹¹	X

Boehringer Ingelheim BI Trial No.: 1445-0011

30 June 2021

c34388550-04 Trial Protocol Page 5 of 75

Proprietary confidential information © 2021 Boehringer Ingelheim International GmbH or one or more of its affiliated companies

Subject must be informed and written informed consent obtained prior to starting any screening procedures. Screening
procedures include physical examination, ophthalmological examination (exclusion of ocular disorders), check of vital
signs, assessment of body temperature, ECG, safety laboratory (including drug screening and infectious serology),
demographics (including determination of body height and weight, smoking status and alcohol history), relevant
medical history, concomitant therapy and review of inclusion/exclusion criteria.

- 2. The time is approximate; the procedure is to be performed and completed within the 3 h prior to drug administration. Allocation to treatment may be performed at any time following enrolment but must be completed prior to first drug administration.
- 3. If several actions are indicated at the same time, the intake of meals will be the last action.
- 4. At the end of trial visit the EoTrial examination includes physical examination, ophthalmological examination (exclusion of ocular disorders), body weight, vital signs, assessment of body temperature, ECG, safety laboratory, recording of AEs, and concomitant therapies.
- 5. Only urine drug screening and alcohol breath test will be done at this time.
- AEs and concomitant therapies will be recorded throughout the trial, but will be specifically asked for at the times indicated in the Flow Chart above.

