# 3.2 DISCUSSION OF TRIAL DESIGN, INCLUDING THE CHOICE OF CONTROL GROUP(S)

For relative bioavailability trials, the crossover design is preferred because of its efficiency: since each subject serves as his own control, the comparison between treatments is based on an intra-subject comparison, thus removing inter-subject variability from the comparison between treatments [R94-1529].

Blinding is not possible because the treatments are distinguishable. The open-label treatment is not expected to bias the results, since the PK endpoints are derived from measurement of plasma concentrations of the analyte which are provided by a bioanalytical laboratory that is blinded to treatment allocation.

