#### 4.1.5 Blinding and procedures for unblinding

This Phase I trial will be handled in an open fashion throughout (that is, during the conduct, including data cleaning and preparation of the analysis). This is considered acceptable because the potential for bias seems to be low and does not outweigh practical considerations.

All trial data will be handled open label. This means that trial functions of the sponsor are unblinded (e.g. clinical trial lead, data manager, statistician, bioanalyst, pharmacokineticist, pharmacometrician, drug metabolism scientist as well as dedicated personnel of the trial site).

Emergency envelopes will not be provided, because the dose of trial medication is known to investigators and subjects.

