#### **6.2.2** Treatment periods

Each subject is expected to participate in 2 treatment periods. At least 8 days will separate drug administrations in the first and second treatment periods.

On Day 1 of each treatment period, study participants will be admitted to the trial site and kept under close medical surveillance for at least 48 h following drug administration. The subjects will then be allowed to leave the trial site after formal assessment and confirmation of their fitness. On all other study days, subjects will be treated in an ambulatory fashion.

Page 55 of 75

Proprietary confidential information © 2021 Boehringer Ingelheim International GmbH or one or more of its affiliated companies

For details on time points and procedures for collection of plasma samples for PK analysis, refer to Flow Chart and Section 5.3.2.

The safety measurements performed during the treatment period are specified in Section 5.3 of this protocol and in the Flow Chart. For details on times of all other trial procedures, refer to the Flow Chart. AEs and concomitant therapy will be assessed continuously from screening until the end of trial examination.

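### Does the minimum tube label, which names no visit or period, put the fed and fasted samples at risk of being confused?

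*Protocol*

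**What the plan says.** Protocol 5.3.2.1 sets the minimum content of the label: "the sample tube labels should list BI trial number, subject number, day, and planned sampling time". It adds: "Further information such as matrix and analyte may also be provided".

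The Flow Chart uses one block of rows for Visits 2 and 3, described as "two identical periods separated by a washout of at least 8 days between drug administrations". Its planned times are relative to drug administration. Day numbers restart: section 6.2.2 says "On Day 1 of each treatment period, study participants will be admitted to the trial site", and footnote B to Table 5.2.4: 1 places Day 2 and Day 5 at both visits.

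On traceability, section 5.3.1 says: "Date and clock times of drug administration and pharmacokinetic sampling will be recorded in the CRFs". Section 5.3.2.1 also requires the time at which each aliquot goes into the freezer to be documented.

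On blinding, section 3.2 accepts the open-label design because concentrations are "provided by a bioanalytical laboratory that is blinded to treatment allocation". Section 4.1.5 says that "trial functions of the sponsor are unblinded (e.g. clinical trial lead, data manager, statistician, bioanalyst, pharmacokineticist" and further roles.

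**The concern.** The four required label items do not include the one fact that separates a subject's two profiles. The optional items named, matrix and analyte, do not separate them either. Every subject takes one period fed and one fasted, so each label text that repeats belongs to one fed and one fasted sample.

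Two things would be at stake. One is the primary comparison of AUC0-tz and Cmax, which is made within subject. If tubes were exchanged between periods, that subject's treatment difference would be distorted, and the exclusion rule for a predose concentration above 5% of Cmax (section 7.3) could be applied to the wrong period. The other is the laboratory blind. If the label does not identify the period, something else must, and the protocol does not say that this is the visit number and not the treatment. Section 4.1.5 adds to the unease by listing the bioanalyst as unblinded while section 3.2 calls the laboratory blinded.

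**Working it through.** **How many samples share a label text**

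- PK time points per period (Flow Chart): predose; 0.25, 0.5, 0.75, 1, 1.25, 1.5, 2, 2.5, 3, 4, 6, 8, 12 h; 24, 34, 48, 72, 96, 120, 144, 168 h. That is 1 + 13 + 8 = 22.
- Planned samples: 22 × 2 periods × 14 subjects = 616.
- Distinct combinations of subject, day and planned time: 22 × 14 = 308, each used twice.
- With the visit number added: 22 × 14 × 2 = 616 distinct labels. The visit number alone does not reveal fed or fasted status to anyone without the randomisation list.

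The count is right for a label that carries the minimum and nothing else. Nothing in the documents says that any tube does.

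**What an undetected exchange would do (scale only)**

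Assume that both complete profiles of one subject are exchanged, that the sequences are balanced 7 + 7, and that there is no period effect. That subject's log difference changes sign, so the average of 14 log differences becomes (13 − 1)/14 = 12/14 of its true value. The estimated ratio is then θ^(12/14).

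| True T/R | Estimated T/R | Shift |
|---|---|---|
| 1.00 | 1.000 | none |
| 0.90 | 0.914 | +1.5% |
| 0.80 | 0.826 | +3.2% |
| 0.60 | 0.645 | +7.6% |

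For the interval, take the protocol's gCV of 23% (section 7.7).

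- The plan's own figure is a factor of 1.224 for N = 14 (Table 7.7: 1), reached with 95% probability. It reproduces as 1.2244, using the t quantile with 12 df and the 95% chi-square bound on the variance.
- The typical factor, without that bound: σ_w = √ln(1 + 0.23²) = 0.2270; SD of a within-subject difference = √2 × 0.2270 = 0.321; t(0.95, 12 df) = 1.782; factor = exp(1.782 × 0.3211/√14) = 1.165.
- One exchanged subject adds (6/7)(2 ln θ)² to the residual sum of squares of the differences, 12 × 0.3211² = 1.237. For θ = 0.90 this is (6/7)(0.2107)² = 0.038, and the factor becomes 1.168. For θ = 0.80 it becomes 1.177, and for θ = 0.60 it becomes 1.222.

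Section 4.1.2 expects exposure to be minimally affected by food. On that expectation the relevant rows are those near 1.00, where the shift is close to zero. The 0.60 row has no basis in the documents and only marks a far end. A full exchange also requires all 22 pairs to be swapped together, because label texts repeat only time point by time point.

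**What separates the tubes in practice**

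- Section 5.3.2.1 sets a floor and allows more. Matrix and analyte are given as examples, not as a closed list.
- The two tubes of a pair are drawn at least 8 days apart at a single centre (SAP 6.5), with date and clock time in the CRF and a documented freezer time for each aliquot.
- The protocol and SAP hand PK data handling to sponsor procedures. One of these is a manual on analytical transfer files (SAP section 7, reference 8), which may define a sample identifier. Its content is not available here.

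**The case for a change.** The strongest case for acting is that a minimum which cannot identify a sample does not do its job, and that one added item would cure it. CRF dates are not on the tube, so they do not by themselves tell two identical labels apart. Second aliquots travel separately, after the first have been acknowledged, and samples may be kept for up to 5 years after the report is archived. Any reliance on shipment records must hold across all of that. In addition, 5.3.2.1 has the bioanalyst acknowledging arrival of the first aliquot, so a role name on the unblinded list also appears at sample receipt.

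The textual part of this stands: the minimum list does omit the visit, and adding it would be harmless. The consequences do not follow. For results to go wrong, a site would have to print only the minimum on tubes for a two-period crossover, and the laboratory would have to accept duplicate labels without a query. For the blind to be lost, someone would have to answer such a query with the treatment, which section 3.2 already rules out. Sections 3.2 and 4.1.5 are compatible if the unblinded bioanalyst is a sponsor role distinct from the staff who generate the concentrations. The wording could be clearer, but it does not show that the blind is lost.

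**Conclusion.** No change to the plan is needed. The protocol leaves a sample-handling detail to the site, the laboratory and the sponsor's procedures, and the sensible way to fill it, a visit or sample number on the tube, is allowed by the text as it stands. If the labels in use already carry it, nothing would differ in practice. No endpoint, model, sample size or analysis rule depends on the point.

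The size is bounded only by assumption. One fully exchanged subject of 14 would move a ratio of 0.90 to 0.914 and leave 1.00 unchanged, given balanced sequences and no period effect. The probability of an exchange cannot be estimated from the documents, and duplicate labels would usually be noticed and queried. The conclusion rests on ordinary crossover practice at the site and laboratory. It would need another look only if the labels actually used carried nothing beyond the minimum, with no other sample identifier.
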